The progress of all patients through the trial will be displayed as part of the CONSORT flow diagram. The number of patients who did not receive the allocated intervention will be reported, including corresponding reasons. Number of patients for whom no endpoints could be collected due to early withdrawal, and reasons for withdrawal, will be reported per trial phase. Patients who died will receive a score of 0 for the primary outcome and will be included in the final analyses, as described in the EQ-5D-5L user guide provided by the EuroQol Research Foundation. (6)

Baseline patient characteristics

The baseline characteristics in Table 1 will be summarized per treatment arm.

Age	Sex	BMI
Type of admission	Admission diagnosis system	ICU admission due to COVID-19 infection
Sepsis	Acute kidney injury	Glasgow Coma Scale
History of diabetes mellitus	APACHE II score	APACHE IV score
SAPS II score	SOFA score	EQ-5D-5L health utility score
Charlson Comorbidity Index	Rockwood Frailty Score	NRS-2002 score

Table 1. Baseline characteristics of the PRECISe trial.

BMI, Body Mass Index; ICU, Intensive Care Unit; COVID-19, Coronavirus Disease 2019; APACHE, Acute physiology and chronic health evaluation; SAPS, Simplified Acute Physiology Score; SOFA, Sequential Organ Failure Assessment; EQ-5D-5L, Euro-QoL-5D-5-level; NRS-2002, Nutritional Risk Screening 2002.

Section 5. Analysis

The purpose of this Statistical Analysis Plan (SAP) is to provide a comprehensive and detailed description of the methods of data analyses proposed for the PRECISe trial. This SAP is based on the study protocol version 5.0 (the Netherlands) and 4.0 (Belgium). The SAP is written in concordance with the guideline for statistical analysis plans, formulated by Gamble et al. (7)

The SAP will define the analyses that will minimally be executed. Statistical analysis will be performed under the responsibility of the authors of the SAP, under the supervision of the trial statistician, while following the statistical principles as formulated in the International Council for Harmonisation (ICH) guideline. (8) This SAP is reviewed and approved by the Trial Steering Committee.

Outcome definitions

Primary outcome

The primary outcome is health-related quality of life, assessed by the overall difference in EQ-5D-5L health utility score between the intervention and control groups over three time points (30, 90, and 180 days after ICU admission), adjusted for baseline EQ-5D-5L.

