- Domain data EQ-5D-5L: scores of subdomains of EQ-5D-5L at 30, 90, and 180 days after admission, with higher scores indicating increased impairment.
- Return to work: number of patients who return to work, and number of days between ICU admission and return to work.

Outcomes regarding protocol adherence are discussed separately under "Adherence and protocol deviations".

Lastly, a health economic evaluation will be performed. Details of this analysis are discussed separately under "Additional analyses".

Unblinding

To mitigate the consequences of an accidental unblinding during the trial, 4 randomization labels (A, B, C, D), were used. Each study group was coded by two different labels. The trial will be unblinded in a stepwise manner. After database lock, it will be revealed which two labels, , each belong together to form one of the groups (i.e., either the high protein or the standard protein group), but it will not yet be revealed which group they actually belong to. Therefore, subsequent analysis of the endpoints will be performed blinded. Only after the analyses are finalized, it will be revealed which group of labels is the high protein group and which group is the standard protein group. This way, the analyses will be done in a blinded fashion, preventing bias.

Analysis methods

Primary outcome

The primary outcome will be analyzed using a linear mixed effects model with a 3-level structure, i.e., repeated measurements are clustered within participants and participants are clustered within centers. The fixed factors are treatment group, time, treatment group*time, and baseline EQ-5D-5L.

With respect to the random-effects, two models will be considered: a random intercepts model and a random intercepts and slope model. The model with the lowest Akaike Information Criterion (AIC) will be selected. Correlations between follow-up measurements will be modelled either using an autoregressive model of the first order (AR1) or left unstructured. Again, the AIC will be used to select the model with the best fit to the data.

Homoscedasticity of the residuals will be assessed using Levene's test and inspected using residual plots. Normality of the residuals will be assessed using QQ-plots. In case of violation of homoscedasticity, the model will be extended with a variance function; in case of violation of normality, the outcome will be transformed. If the assumption is still violated after transformation, we will apply a robust mixed-effects fit.

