As sensitivity analysis, the model will be further adjusted for sex, APACHE II score, APACHE IV admission diagnosis, and NRS-2002.

Secondary and tertiary outcomes

Survival outcome

For the secondary endpoint overall survival, survival curves for both treatment arms will be constructed using the Kaplan-Meier method. Then, a Cox proportional hazards frailty model, with a 2-level structure, i.e., participants clustered within centers, will be used to investigate a treatment effect. The crude, unadjusted Hazard ratios will be reported with a 95% confidence interval. The proportional hazard assumption will be assessed as the association between the scaled Schoenfeld residuals and follow-up time. Additionally, sensitivity analyses will be performed by adjusting for potential confounders (sex, APACHE II score, APACHE IV admission diagnosis, and NRS-2002) is similar as described for the primary endpoint analysis.

Longitudinally assessed outcomes

The treatment effects for longitudinally assessed secondary and tertiary endpoints (SF-36, HADS, IES-R, EQ-5D-5L (EQ-VAS and pain question), 6-minute walking distance, MRC-SUM, and handgrip strength, frailty assessed by Rockwood Clinical Frailty Scale and mean and maximum SOFA scores) are assessed using linear mixed-effects models. The statistical approach will be similar as described for the analysis of the primary endpoint, particularly concerning the calculation of between-group differences, the 3-level model structure (with fixed treatment effect and random effects for center and participants), reporting of effect size, adjustment for potential confounders, and model selection strategy.

Time-to-event outcome

For time-to-discharge-alive from hospital, data of non-survivors will be censored at a time point beyond that of the last surviving patient to account for death as a competing risk. Between-group differences will then be estimated similar to overall survival.

Categorical outcomes

The differences in all categorical tertiary outcomes (see **Appendices 3-5**) will be analyzed using Pearson's chi-square test or Fisher's exact test, as appropriate. The treatment effects on all other tertiary outcomes will be analyzed using the Student's t-test or Mann-Whitney U test, depending on the distribution of data.

Subgroup analyses

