The assumed missing data mechanism for all endpoints is missing at random (MAR), given the amount of baseline covariates and other outcome variables collected. Longitudinal endpoints will be analyzed using mixed-effects models. This approach is robust with regard to MAR provided that variables contributing to the mechanism are used as covariates in the model.

In practice, baseline or outcome covariates will be introduced to the model if more than 5% of outcome data are missing. The baseline covariates in Table 1 and other outcome variables will be tested and added to the model if they are associated with the outcome or with a missingness indicator in univariate analysis with a P-value of < 0.05.

Missing data in other outcome data (not longitudinally assessed) and baseline covariates will be imputed using multiple imputation with fully conditional specification, in case the rate of missing data is more than 5%.

As a sensitivity analysis, we will perform the analysis of the primary outcome without modelling the MAR mechanism to test the robustness of our assumption.

Additional analyses

Health economic evaluation

The main question for the economic evaluation is to assess whether high enteral protein provision is cost-effective compared to standard enteral protein provision. The economic evaluation will be performed from a health care perspective over 180 days from ICU admission.

To quantify health care costs, data regarding ICU and hospital resource use will be collected, using the Dutch (Zorginstituut Nederland) and Belgian (RIZIV) guidelines for cost calculation. (14, 15) The following variables will be collected to quantify the most important medical costs within and outside

the hospital incurred by ICU patients: duration of mechanical ventilation, ICU and hospital length of stay, ICU and hospital readmissions, days on renal replacement therapy, days on intravenous antibiotics, complications, and admission to and duration of stay in a rehabilitation center.

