To address the question regarding cost-effectiveness, we will perform a cost-utility analysis. A generic quality of life questionnaire, the EQ-5D-5L, will be taken 30, 90 and 180 days after ICU admission. The EQ-5D-5L scores will be translated to health state utilities with the Dutch and the Belgian value set. (16, 17) Subsequently, a quality-adjusted life year (QALY) will be calculated by multiplying the length of time with the utility scores between time points. The advantage of using a QALY is that it combines reduced morbidity (quality gain) and reduced mortality (quantity gain) in one measure. For 1 year in perfect health, the total maximum QALY will be 1.

Data will be analyzed on an intention-to-treat basis. As most volumes of resources follow a skewed distribution, differences in costs between the two groups will be analyzed with non-parametric bootstrap analysis. Bootstrap analysis will further be used to quantify the uncertainty surrounding the incremental cost-effectiveness ratio (ICER). The results of this analysis will be presented in cost-effectiveness planes and acceptability curves. Missing data will be imputed by a multiple imputation approach. Uncertainty related to the impact of different parameters on the incremental cost-effectiveness ratio will be assessed with uni- and multivariate sensitivity analysis. The trial-based cost-effectiveness analysis will follow the International Society for Pharmacoeconomics and Outcomes Research (ISPOR) guidelines. (18)

Bayesian analysis of primary and secondary outcomes

The proposed secondary, preplanned Bayesian analysis of the PRECISe trial will provide additional information on the effects of high protein on functional and clinical outcomes in critically ill patients, such as probabilistic interpretation, probabilities of clinically important effect sizes, and the integration of prior evidence. As such, it will complement the interpretation of secondary endpoints and subgroup analyses. An extensive protocol for this Bayesian analysis has been published elsewhere. (19)

Outcomes and subgroups

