Given the mixture distribution of the EQ-5D-5L (the component of zero and the component other than 0), we will specify separate priors per longitudinally assessed outcome. Consequently, we will specify a prior for the mean difference with an EQ-5D-5L other than 0 and a prior for the proportion of patients who have an EQ-5D-5L score of 0 (i.e., deceased patients). This longitudinal analysis will be performed with adjustment for center as a random effect. The results of the analyses for the components will be presented separately and as weighted averages.

Analysis of longitudinally assessed secondary outcomes

Secondary outcomes for which no prior evidence was available will be estimated under a weakly informative prior, in a model similar to the longitudinally assessed primary outcome, with adjustment for the random effect of center.

Analysis of outcomes at one given time point

Secondary binary outcomes, such as 60-day mortality, will be expressed in ORs and absolute risk differences (ARD). These binary outcomes will be analyzed in a binary mixed regression model (Bernoulli distribution) with an adjustment for the random center effect. Priors for these binary outcomes are presented on the log OR scale in Table 1. Other secondary continuous outcomes, such as the duration of mechanical ventilation, will be reported in mean differences (MD) for the specific units of that endpoint. Finally, the abovementioned mixture distribution (the component of zero, and the component other than 0) will be used for the EQ-5D-5L assessment at the cross-sectional time points, and separate priors will be formulated, similar to the primary outcome assessment.

Handling of missing data

As the missingness of data is assumed to be missing at random (MAR), the linear mixed effects model will be appropriate to handle missing data.

Model settings and diagnostics

The models for our analysis will be implemented in *JAGS* using Markov Chain Monte Carlo (MCMC) algorithms, through the *R2jags* package (20, 21). Assessment of model convergence will be performed for key model parameters via potential scale reduction factors (Rhat) effective sample size (ESS), and other diagnostics such as density and trace plots. Model fit will be assessed in relative terms through the deviance information criterion (DIC and other criteria alike), and in absolute terms using posterior prediction checks (PPCs).

(Serious) Adverse events

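### The only missing-data sensitivity analysis for the primary EQ-5D-5L outcome checks covariate choice; it cannot detect departures from missing at random that those covariates leave unexplained

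*SAP*

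**What the plan says.** Section 5, Missing data, assumes MAR for all endpoints and relies on mixed models for the longitudinal ones. The mechanism is modelled through covariates: "baseline or outcome covariates will be introduced to the model if more than 5% of outcome data are missing". Candidates are the baseline variables and other outcome variables, selected by univariate P < 0.05. The sensitivity analysis then repeats the primary analysis "without modelling the MAR mechanism to test the robustness of our assumption".

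The base model is under Analysis methods, Primary outcome: "The fixed factors are treatment group, time, treatment group*time, and baseline EQ-5D-5L".

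Other places that bear on missing scores:

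- Primary outcome: "As sensitivity analysis, the model will be further adjusted for sex, APACHE II score, APACHE IV admission diagnosis, and NRS-2002".
- Missing data: "Missing data in other outcome data (not longitudinally assessed) and baseline covariates will be imputed using multiple imputation with fully conditional specification", when more than 5% are missing.
- Health economic evaluation: "Missing data will be imputed by a multiple imputation approach".
- Bayesian analysis, Handling of missing data: "As the missingness of data is assumed to be missing at random (MAR), the linear mixed effects model will be appropriate".
- Withdrawal/follow-up: "Patients who died will receive a score of 0 for the primary outcome".
- Sample size: actual loss to follow-up is 9.4%, against 5% planned, with a revised target of 935 patients.

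**The concern.** The SAP presents the refit as a test of the MAR assumption, yet both analyses in the comparison depend on MAR. If patients who do not return the questionnaire are in worse (or better) health than their recorded data predict, and more so in one arm, both estimates carry that error and may still agree. A reader could then take agreement as support for MAR when it shows only that covariate choice matters little.

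Known deaths always have a value of 0. Missing scores therefore come from patients who are alive, or whose vital status is unknown after withdrawal. In such patients, health itself may plausibly influence whether a questionnaire is completed. At stake is how far the primary conclusion can be trusted with nearly one patient in ten lost.

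**Working it through.** **1. The plan's own figures.** With SD 0.30, difference 0.06, two-sided alpha 5% and 80% power, n per arm = 2 × (0.30 × 2.8016 / 0.06)² = 392.4; the SAP has 392. For loss, 784 × 1.05 = 823.2, which gives 824 as stated (784 / 0.95 would give 826). The revised 935 came from a simulation on trial data that the SAP does not contain, so it cannot be reproduced. None of this affects the point below. Expected loss is 0.094 × 935 = 87.9, about 88 patients.

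**2. What the refit is.** In the Missing data section, modelling the mechanism means adding covariates. Leaving them out returns the base mixed model, a likelihood analysis valid under MAR given treatment, time and baseline EQ-5D-5L. This is an inference from the text. If complete cases were meant, the assumption would be stronger and the limitation would remain. At 5% missing or less no covariates are added for missingness, so the refit would be the main analysis again; the reported 9.4% makes that unlikely.

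**3. What the comparison can see.** Let m be the share missing at all visits in each arm. Let δ be the amount by which one arm's missing scores lie below the base model's prediction, relative to the other arm, and f the fraction of δ that the added covariates explain.

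- Error of the refit = m × δ
- Error of the main analysis = (1 − f) × m × δ
- Gap between the two = f × m × δ

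With m = 0.094 and δ = 0.2, m × δ = 0.0188:

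| f | Gap | Error left in main analysis |
|---|---|---|
| 0 | 0 | 0.0188 |
| 0.25 | 0.0047 | 0.0141 |
| 0.50 | 0.0094 | 0.0094 |
| 1 | 0.0188 | 0 |

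For a given δ, the gap is smallest where the main analysis is most wrong.

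A simulation of the case f = 0 agrees. It used 50 runs of 40,000 patients, about 9.5% lost, and a covariate related to both loss and outcome; it had no deaths and no centre level, and analysed the patient mean over three visits. With one-arm deficits of 0, 0.1, 0.2 and 0.3, the fits with and without the covariate differed by at most 0.0002. Both were in error by about 0, 0.009, 0.019 and 0.029.

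**4. Size.** Here δ is the part left unexplained, so shift = m × δ. Missing at day 180 only, the shift on an equally weighted three-visit average is m × δ / 3. The δ values are assumptions, and so is the range for m, because the SAP gives no breakdown of loss.

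| Missing per arm | δ = 0.1 | δ = 0.2 | δ = 0.3 |
|---|---|---|---|
| 5%, all visits | 0.005 (8% of 0.06) | 0.010 (17%) | 0.015 (25%) |
| 9.4%, all visits | 0.009 (16%) | 0.019 (31%) | 0.028 (47%) |
| 15%, all visits | 0.015 (25%) | 0.030 (50%) | 0.045 (75%) |
| 9.4%, day 180 only | 0.003 (5%) | 0.006 (10%) | 0.009 (16%) |

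Equal departures with equal loss in both arms give no shift.

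**5. Against significance.** The stated 80% power for 0.06 implies SE = 0.06 / 2.8016 = 0.0214 and a critical difference of 1.96 × 0.0214 = 0.042. With the SE held fixed and scores missing at all visits, an estimate of 0.05 (p = 0.020) loses significance at δ = (0.050 − 0.042) / 0.094 = 0.085. An estimate of 0.06 (p = 0.005) does so at 0.018 / 0.094 = 0.19. With only day 180 missing, these become about 0.26 and 0.58.

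**6. Whether another analysis fills the gap.** The adjusted sensitivity model only adds baseline covariates. Multiple imputation is confined to outcomes not assessed longitudinally and to baseline covariates. The cost-utility imputation states no departure from MAR. The Bayesian analysis assumes MAR, and its text on priors describes the trial's analysis as complete-case with non-survivors included. None explores a departure from MAR.

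**The case against.** The refit is not worthless. The SAP states MAR as conditional on the variables collected, and dropping them does probe dependence on that set. Where they explain part of the departure, the two fits separate. No analysis of observed data can verify MAR, and a delta analysis only explores assumed departures. This stands: the defect is limited reach and a purpose stated too broadly.

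The larger shifts need a departure in one arm relative to the other, with scores missing at every visit. Blinding and the use of four labels make a large arm-specific departure less likely, though they do not exclude it. This stands as a limit on importance.

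The scale of δ also matters. Above, it is measured from the MAR prediction, and for patients missing at every visit that prediction blends in the zeros for deaths. Assume 30% to 40% deaths, all lost patients alive, and a survivor mean of 0.5 to 0.7. The prediction then lies between (0.30 / 0.906) × 0.5 = 0.17 and (0.40 / 0.906) × 0.7 = 0.31 below observed survivors. A δ of 0.3 on this scale is therefore a much larger deficit relative to fellow survivors, and true scores could lie on either side of the prediction. The figures above hold only as between-arm differences in departure, and a new analysis must say where its delta starts.

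The SAP already commits to reporting withdrawals and their reasons by trial phase. That describes the loss but does not test its effect on the estimate.

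**Conclusion.** The point holds in a limited form. The refit shows how far the primary result depends on the chosen covariates. It cannot detect departures from MAR that those covariates leave unexplained, and nothing else in the SAP does so. This is true under either reading of the refit.

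With 9.4% missing at all visits and a between-arm departure of 0.1 to 0.3, the shift is 0.009 to 0.028, or 16% to 47% of the 0.06 target. It is about a third of that for day 180 alone, and nil with equal departures and equal loss. These rest on assumed departures and on equal loss per arm.

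A reader might infer that the refit can show no departure at all, or that the primary estimate is biased by up to half the target difference. The documents support neither. The refit can reveal the explained part, and without loss by arm, visit and vital status the actual bias is unknown. Nor does the SAP say that agreement will be reported as proof of MAR; it only gives the refit the purpose of testing it. Importance is moderate: the SAP should be changed, but the primary model need not be.

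**What to change.** Keep the primary model. In the Missing data section:

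1. Describe the refit without added covariates as a check on covariate choice, and state which model it is.
2. Add a prespecified delta-adjusted multiple-imputation (tipping-point) analysis of the primary outcome. Impute missing EQ-5D-5L by arm among patients known to be alive at the visit, keep deaths at 0, and vary vital status where it is unknown.
3. State that delta is measured from the values imputed for living patients. Apply it in stated steps (for example 0.05 to 0.30) in one arm and in both arms, fit the primary model to each set, and report where the conclusion changes.

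The cost is SAP wording and modest programming and analysis time. No new data are needed: Appendix 5 already records whether and when a patient died, and why and when participation ended early.

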The PRECISe trial is a bi-national, quadruple-blinded, multicenter randomized controlled trial (RCT) assessing the superiority of high versus standard enteral protein provision in mechanically ventilated ICU patients. (2)

Randomization

A computer algorithm was used to generate the concealed, random allocation sequence. Patients were randomized in a 1:1 ratio, stratified per center, using block randomization with random permuted block sizes varying between 4 and 6.

Sample size

The sample size calculation was based on a published cross-sectional measurement of the EQ-5D-5L health utility score at 180 days following ICU admission, as longitudinal data were unavailable (3). A minimum difference of 0.06 points on the EQ-5D-5L health utility score was selected to represent the minimum clinically important between-group difference to be detected. (4)

Based on these data, the sample size for the PRECISe trial was calculated as follows: assuming a standard deviation (SD) of 0.3 at 180 days (3), considering a two-sided type I error rate α of 5% and a type II error rate β of 20% (yielding a statistical power of 80%), 392 participants per intervention group will be required to detect the minimum clinically important difference of 0.06 in the EQ-5D-5L health utility score. In line with other critical care trials, the sample size has been adjusted upwards for an estimated 5% loss to follow-up for the primary endpoint. (5) After this adjustment, the final sample size for the PRECISe trial was set at 824 participants.

During the preplanned interim safety analysis after inclusion of 50% of patients, it became apparent that mortality was higher than anticipated, resulting in a standard deviation of the EQ-5D-5L HUS that was larger than expected (0.38 vs 0.30). Since this potentially could reduce the power of the study, the DSMB advised to increase the sample size. By running a Monte Carlo simulation of the primary outcome analysis using raw longitudinal data of the actual study population at that time (n = 709), without unblinding, it was calculated that with the observed standard deviation, a sample size of 935 patients would be required to retain 80% power to detect the minimally important difference of 0.06, while correcting for the actual loss-to-follow-up rate of 9.4%.

Framework

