For each endpoint, a minimal clinically important difference (MCID) is derived from the literature (see Table). For all analyses, we will use weakly informative priors centred around 'no effect' (mean difference [MD] of 0, or an odds ratio [OR] of 1 [0 on the log OR scale]). For the binary outcomes (ORs, denoted as the log of the OR), a mean of 0 will be applied for the weakly informative prior, while the standard deviation (SD) will be set to 3 on the log OR scale to capture all credible effect sizes. For the continuous outcomes (on the MD scale), we aim to be consistent and reproducible, but will also allow the distributions to capture all plausible effect sizes. As such, the standard deviation (SD) will be based on a multiplication of the MCID (x100). Table 1 presents the numerical values of these weakly informative priors. Skeptical and enthusiastic priors are defined following a modification of the approach suggested by de Grooth and Elbers. (23) Skeptical priors will be centred at a mean difference (MD) or log OR of 0. The distribution will incorporate a <10% probability that the estimated treatment effect will exceed +1 MCID. Conversely, the enthusiastic priors are centred around an effect of +2 MCID and will follow a similar distribution with a probability of <10% that the estimated effect size will be smaller than +1 MCID.

Outcome	Effect size and approach	Weakly informative	Literature-based* (mean, SD)	MCID	Ref.
Primary outcome				·	
EQ-5D-5L HUI (>0)	MD, longitudinal	(0, 6.0)	NA	0.06	(2)
EQ-5D-5L HUI (0)	OR, longitudinal	(0, 3.0)	NA	0.06	(2)
Secondary outcomes				1	1
6MWT (m)	MD, longitudinal	(0, 1900)	NA	19 m	(24)
HGS (kg)	MD, longitudinal	(0, 500)	NA	5.0 kg	(25)

Duration of MV (days)	MD, cross-sectional	(0, 100)	(-0.42, 0.30) days	1.0 days	(26)
60-day mortality	OR, cross-sectional	(0, 3.0)	(-0.02, 0.09)	5% ARD	(27)
		Log-scale, OR	Log-scale, OR		
EQ-5D-5L HUI	MD, cross-sectional	(0, 6.0)	NA	0.06	(2)
30 days (>0)					
EQ-5D-5L HUI	OR, longitudinal	(0, 3.0)	NA	0.06	(2)
30 days (0)					
EQ-5D-5L HUI	MD, cross-sectional	(0, 6.0)	NA	0.06	(2)
90 days (>0)					
EQ-5D-5L HUI	OR, longitudinal	(0, 3.0)	NA	0.06	(2)
90 days (0)					
EQ-5D-5L HUI	MD, cross-sectional	(0, 6.0)	NA	0.06	(2)
180 days (>0)					
EQ-5D-5L HUI	OR, longitudinal	(0, 3.0)	NA	0.06	(2)
180 days (0)					
Subgroup analyses			I		
EQ-5D-5L HUI	MD, longitudinal	(0, 6.0)	NA	0.06	(2)
Sepsis (>0)					
EQ-5D-5L HUI	OR, longitudinal	(0, 3.0)	NA	0.06	(2)
Sepsis (0)					

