EQ-5D-5L HUI	MD, longitudinal	(0, 6.0)	NA	0.06	(2, 28)
Non-sepsis (>0)					
EQ-5D-5L HUI	OR, longitudinal	(0, 3.0)	NA	0.06	(2, 28)
Non-sepsis (0)					
EQ-5D-5L HUI	MD, longitudinal	(0, 6.0)	NA	0.06	(1, 2)
AKI (>0)					
EQ-5D-5L HUI	OR, longitudinal	(0, 3.0)	NA	0.06	(1, 2)
AKI (0)					
EQ-5D-5L HUI	MD, longitudinal	(0, 6.0)	NA	0.06	(1, 2)
Severe multi-organ					
failure (>0)					
EQ-5D-5L HUI	OR, longitudinal	(0, 3.0)	NA	0.06	(1, 2)
Severe multi-organ					
failure (0)					

For the cross-sectional endpoints "60-day mortality" and "duration of mechanical ventilation", informative priors could be derived from a meta-analysis of randomized trials addressing the clinical effectiveness of high protein nutrition in critical illness (29), which the same authors have recently updated after the publication of the EFFORT Protein trial (1). The authors kindly shared data from this updated meta-analysis that are relevant to the current Bayesian analysis protocol prior to publication. This meta-analysis also contains one study that reports on EQ-5D-5L (31), albeit on a survivors-only analysis. Since the PRECISe trial uses a complete-case analysis (including non-survivors), these data could not be used to formulate a reasonable literature-based prior for the estimation of the treatment effect on this outcome. Therefore, cross-sectional and longitudinal analyses of EQ-5D-5L will be performed under weakly informative priors, skeptical priors, and enthusiastic priors.

As all analyses will be performed with adjustment for the random center effect, a prior for this effect is uniformly formulated as well. These models incorporate random intercepts and the prior for these random effects follow a normal distribution with an effect centered around a mean of 0 and a large standard deviation, similar to the other priors.

If evidence from additional relevant randomized trials on high protein provision will be published before executing this Bayesian analysis, we will consider incorporating these data in the literaturebased priors.

Presentation of results and summary statistics

Posterior distributions will be presented as MDs or mean ARDs and median OR, accompanied by 95% credible intervals (CrI) with reference to the used priors.

Analysis of the primary outcome (EQ-5D-5L over 180 days)

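### Bayesian prior table: the eight odds-ratio rows for the death component of EQ-5D-5L carry a utility-point MCID (0.06), so their skeptical and enthusiastic priors are on the wrong scale

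*SAP*

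**What the plan says.** The Sample size section of the SAP fixes the meaning of 0.06: "A minimum difference of 0.06 points on the EQ-5D-5L health utility score was selected". It is a between-group difference in mean utility.

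In the Bayesian section, the Priors subsection states: "For each endpoint, a minimal clinically important difference (MCID) is derived from the literature (see Table"). Three rules there use MCIDs:

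- Weakly informative prior, continuous outcomes: "the standard deviation (SD) will be based on a multiplication of the MCID (x100"). For odds-ratio outcomes the SD is instead fixed at 3 on the log odds-ratio scale.
- Skeptical prior: centred at no effect, with the spread set by "The distribution will incorporate a <10% probability that the estimated treatment effect will exceed +1 MCID".
- Enthusiastic prior: "the enthusiastic priors are centred around an effect of +2 MCID", with less than 10% probability below +1 MCID.

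The Bayesian subsection on the primary outcome describes the zero component as needing "a prior for the proportion of patients who have an EQ-5D-5L score of 0 (i.e., deceased patients"). It adds: "The results of the analyses for the components will be presented separately and as weighted averages".

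The prior table has eight rows marked (0): overall, days 30, 90 and 180, sepsis, non-sepsis, AKI and severe multi-organ failure. Each has an odds ratio as its effect measure, (0, 3.0) as its weakly informative prior and 0.06 as its MCID. The only other odds-ratio row, 60-day mortality, has an MCID of 5% absolute risk difference (ARD). The priors are to be used: analyses of "EQ-5D-5L will be performed under weakly informative priors, skeptical priors, and enthusiastic priors".

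**The concern.** A difference of 0.06 utility points says nothing about what change in the odds of death matters. The table itself suggests that the figure was carried over: each (0) row repeats the 0.06 and the references of its paired mean-difference row, whereas 60-day mortality has its own risk-scale MCID with its own reference.

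The SAP prints no numerical skeptical or enthusiastic prior. For the death component, the skeptical SD and the enthusiastic centre and SD come from the MCID alone, so all three rest on a figure from another scale. These priors are the stated robustness check. The death component is reported on its own and also inside the weighted average, so under these priors the fault reaches the combined Bayesian EQ-5D-5L result too.

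If the scale is left open until the analysis is run, someone must choose between readings that give very different priors.

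**Working it through.** **Which scale is 0.06 on?** Apply the rule for continuous outcomes, SD = 100 × MCID, to the mean-difference rows:

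- EQ-5D-5L: 100 × 0.06 = 6.0
- 6-minute walk: 100 × 19 = 1900
- handgrip: 100 × 5.0 = 500
- ventilation: 100 × 1.0 = 100

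All four match the printed values, so 0.06 in the mean-difference rows is the utility MCID. The (0) rows repeat it with no unit or conversion.

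**Inputs.** N = 935 (Sample size section). Assumed, because the SAP does not give it: 30–45% with score 0. Also assumed: observed odds ratios of 0.75, 0.90, 1.00 and 1.10. The calculation is a normal approximation at one time point for the whole trial, without centre effects or repeated measures.

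**Formulas.**

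- Prior SD = MCID / 1.2816. This is an upper bound, because the rule says less than 10%.
- SE of the log OR = √(4 / (N·p·(1−p))), which is 0.143 at p = 0.30 and 0.131 at p = 0.45.
- Data weight w = SD² / (SD² + SE²).
- Posterior mean = w·ln(OR) for the skeptical prior, and w·ln(OR) − (1−w)·2·MCID for the enthusiastic prior, taken toward benefit.
- Posterior SD = (1/SD² + 1/SE²)^(−½).
- Pr(OR<1) = Φ(−mean / posterior SD).
- An ARD of d converts to logit(p) − logit(p−d).

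**Worked case: 0.06 read as a log OR, p = 0.30, observed OR 0.75.** SD = 0.06 / 1.2816 = 0.0468. w = 0.00219 / (0.00219 + 0.02037) = 0.097. Mean = 0.097 × (−0.288) = −0.028. Posterior SD = 0.0445. Pr(OR<1) = Φ(0.63) = 0.73.

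**Ranges over p = 0.30–0.45.**

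| | 0.06 as log OR | 5-point ARD | 6-point ARD |
|---|---|---|---|
| MCID as log OR | 0.06 | 0.205–0.251 | 0.247–0.305 |
| Skeptical SD (at most) | 0.047 | 0.16–0.20 | 0.19–0.24 |
| Data weight | 10–11% | 60–65% | 68–74% |
| Skeptical Pr(OR<1), OR 0.75 | 0.73–0.77 | 0.95 | 0.96–0.97 |
| Skeptical Pr(OR<1), OR 0.90 | 0.59–0.61 | 0.73 | 0.74–0.75 |
| Skeptical Pr(OR<1), OR 1.00 | 0.50 | 0.50 | 0.50 |
| Skeptical Pr(OR<1), OR 1.10 | 0.40–0.42 | 0.29–0.30 | 0.28 |
| Enthusiastic centre (OR) | 0.89 | 0.61–0.66 | 0.54–0.61 |
| Enthusiastic Pr(OR<1), OR 0.90 | >0.99 | 0.98–0.99 | 0.97–0.98 |
| Enthusiastic Pr(OR<1), OR 1.00 | 0.99 | 0.93–0.95 | 0.91–0.93 |
| Enthusiastic Pr(OR<1), OR 1.10 | 0.99 | 0.83–0.86 | 0.77–0.80 |

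At an observed OR of 0.75 the enthusiastic probability exceeds 0.99 in every column.

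**Two checks on the log OR reading.** Converted back, a log OR of 0.06 is an ARD of 1.24 points at p = 0.30 and 1.48 at p = 0.45, or 25–30% of the 5 points used for 60-day mortality. A prior SD of 0.0468 is worth 4 / (p·(1−p)·SD²) patients, about 7,400 to 8,700, against 935 in the trial.

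**Other readings.** An odds ratio of 1.06 gives nearly the same result as the log OR reading (SD 0.045, data weight 9–11%). An odds ratio of 0.06 gives ln(0.06) = −2.81 and an SD of about 2.2, which is implausible as an MCID.

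**The case against.** The strongest reply is that the severe result depends on reading 0.06 as a log odds ratio, which the SAP never states. The log odds-ratio labels describe the priors, not the MCID column, and that column already holds an ARD for 60-day mortality. Read as a 6-point ARD, 0.06 differs little from a 5-point one: skeptical probabilities move by about 0.01 and enthusiastic ones by at most about 0.06. In addition, the SAP refers to a separately published Bayesian protocol that may give usable values, the weakly informative analysis does not use the MCID, and the whole analysis is secondary.

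Part of this stands. The 10–11% data weight is conditional on the log OR (or OR 1.06) reading. The figures describe the whole trial at one time point; four of the eight rows are subgroups of unknown size. The published protocol was not available for this review.

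It does not remove the error. The 6-point reading is not stated either. It needs a control risk that the SAP does not give, and it would set a death MCID different from the 5% used for 60-day mortality, without explanation. A further source may supply values, but it does not correct the figure printed here.

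**Conclusion.** The concern holds. The eight (0) rows print an MCID on the wrong scale, and the SAP builds the skeptical spread and the enthusiastic centre and spread for the death component from it. This follows from the document alone and needs no assumption.

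The size of the effect depends on how 0.06 would be used. As a log odds ratio, it makes both priors narrow enough largely to override the data; an observed OR of 1.10, which points to harm, would still give an enthusiastic probability of benefit of 0.99. As a 6-point ARD, the results would be close to those from 5 points. These sizes rest on N = 935, the assumed 30–45% mortality and the normal approximation.

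The skeptical centre, the weakly informative priors (0, 3.0), the mean-difference rows and the frequentist primary analysis are unaffected. It should be fixed, but it does not threaten the trial's main result.

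**What to change.** In the eight (0) rows, replace 0.06 with a risk-scale MCID for death and give its source; the 5% ARD already used for 60-day mortality is one option. State the control risk used to convert it to a log odds ratio, which the 60-day mortality row needs as well. Print the resulting skeptical and enthusiastic means and SDs, or cross-refer to the exact values in the published Bayesian protocol.

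Two wording changes can be made at the same time. State that +MCID means toward benefit, since a positive log odds ratio for death points to harm. Relabel the (>0) rows as scores other than zero, to agree with the text on the primary outcome.

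The cost is eight table cells and a sentence or two, before the Bayesian analysis is run. No data are needed.
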